4 STUDY DESIGN

This is a cross-sectional study using mixed methods. One hundred and fifty carers of people with a diagnosis of dementia will be recruited to take part in the study. They will take part in a quantitative interview with a range of questionnaires. A smaller purposive sample of 20 of these participants will be invited to take part in a qualitative interview as an additional component. The two components will enable exploration of the objectives listed in section 3.2 above. The content and procedures for each interview is described below. Participants will not be paid to participate in this study.

4.1 Quantitative interviews (n=150)

The study will aim to recruit 150 carers over a 15 month period starting in late 2017. The recruitment and consent process is described in detail in Section 6 and the power calculation in Section 7. Carers will provide written, informed consent before completing a face-to-face interview in a location of their choice. Previous experience in research with carers indicates that the majority will wish to be interviewed in their own home or the home of the person with dementia. Researchers will undertake the interview in pairs to begin with but on their own after training is complete. They will adhere to the UCL lone worker policy.

Researchers will ask questions and record answers on the Case Report Form (Appendix 1). The CRF contains demographic questions about the carer and some basic information about the person with dementia (such as dementia severity, type of diagnosis and time since diagnosis).

The Marwit-Meuser Caregiver Grief Inventory Short Form (MMCGI-SF) [25] will be used to assess severity of grief before death. This scale contains three subscales: heartfelt sadness and longing, worry and felt isolation, and personal sacrifice burden; a cutoff of 70/90 is considered a high level of grief.[25] The Clinical Dementia Rating scale will assess dementia severity based on the carer's report [26]. To test the primary hypothesis we will collect a number of measures to reflect the five modifiable factors that suggest preparation for end of life:

1. Greater knowledge of how dementia progresses (Dementia Knowledge Assessment Scale [27])
2. Greater knowledge of the person with dementia's end of life preferences (Discussed wishes regarding end of life with your relative? Have a good understanding of their wishes for end of life care?)
3. Having a lasting Power of Attorney or other formal advance directives in place - a proxy indication of "preparedness" (binary variable; any form of directive in place/not in place)
4. Higher satisfaction with communication with healthcare providers (Health Literacy Questionnaire [HLQ, excluding Social Support subscale] which examines how well carers understand health information and navigate the health system [28]) (See Appendix 2)
5. Higher satisfaction with support for health from social network (HLQ-Social Support subscale.[28])

A number of other measures have been included for other exploratory analysis and to control for possible confounders. These include:

- Townsend Deprivation Index (identified through the participant's postcode)
- Hospital Anxiety and Depression Scale (HADS) [29]
- Relationship Closeness Scale [30] completed to reflect current relationship as well as relationship prior to dementia [31]
- Subscales (denial, self-blame, acceptance, active coping, humour, and substance abuse) from the Brief Coping Orientation to Problems Experienced scale (Brief COPE) [32]
- Religiosity using the Duke University Religion Index (DUREL) [33]
- Questions about the experience of taking part in the study (See justification and questions in Section 'Assessment and Management of Risk' in this protocol).

After agreeing to a date for the interview carers will be sent the Health Literacy Questionnaire (HLQ) [28] and be encouraged to complete this before the face-to-face interview. The purpose of this is to reduce the time required to complete the face-to-face interview so that it is less burdensome for the carer. The questionnaire is suitable for this purpose as it contains neutral questions about communicating with healthcare professionals.

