Figure 1: Existing evidence linking preparation for end of life and grief (before and after the death)

This will be the first UK study to assess the prevalence of grief before the death amongst a sample of carers for people with all stages of dementia and living either at home or in a care home. It will be one of few studies to explore whether modifiable factors showing preparation for end of life are associated with lower levels of grief before the death. The modifiable factors reflecting preparation for end of life include:

- carers' having a good knowledge of dementia progression,
- high health literacy,
- a lasting (enduring) Power of Attorney,
- knowing the end of life wishes of the person with dementia and
- being satisfied with support from their social network.

Knowing which modifiable factors reflecting preparation for end of life are most closely associated with grief before the death will inform the development of a resource for carers. If this study is successful in developing the first evidence-based intervention for family carers to reduce grief before the death and improve preparation for end of life, it has the potential to reduce carer distress during the lifetime of the person with dementia, bringing benefits for the person with dementia as well as their carer. It will enable discussions to ensure care at the end of life is planned and in accordance with the person's wishes; and may reduce the prevalence of complicated grief after the death of the person with dementia.

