3 OBJECTIVES

3.1 Primary Objective

This study aims to examine the relationship between family and friend carers' feelings of grief before the death of a person with dementia and how well carers are prepared for that death.

The hypothesis that will be tested is that modifiable factors indicating preparation for end of life are associated with lower grief before the death in carers of people with dementia.

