3.2 Secondary Objectives

- To examine the prevalence and severity of grief before the death in carers of people with dementia (Quantitative interviews)
- To identify which modifiable factors reflecting preparation for end of life are most strongly related to grief before the death (Quantitative interviews)
- To examine the extent to which carers feel prepared for the future and end-of-life care for their relative with dementia (Quantitative and qualitative interviews)
- To explore whether carers recognize grief during caring and what supports they think would be helpful (Quantitative and qualitative interviews)
- To identify unmet needs for information about end of life symptoms and emotional support for carers (Qualitative interviews)
- To explore how carers experience and cope with changes in grief over time (Qualitative interviews)

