4.2 Qualitative semi-structured interviews (n=20)

A sub-sample of the 150 carers will be invited to participate in an additional set of semi-structured open-ended questions to enable more in-depth exploration of some of the secondary objectives as outlined in section 3.2 above. The interview will explore the dynamic and changing nature of grief over time, how carers identify with the concept of grief and whether they consider they are going through a grief experience. It will also examine what supports they have found helpful and what they perceive to be unmet information and support needs and possibly programs/resources that might address these needs. The interview guide (Appendix 3) provides a list of questions that will be used as a guide for a fluid conversation that will pick up on areas considered relevant by the participant. Qualitative interviews will be audio-recorded with permission from the participant on an encrypted digital recorder and then transcribed verbatim by the research team.

Participants will be purposively selected to provide a mix of responses representing male and female participants, adult child and spouse participants, different ethnicity as well as carers of people at

different severity of dementia. Participants who agree to participate in the quantitative interviews will also be asked to participate in the qualitative interview after completing the quantitative interview. If the sample is not representing a mix of carers based on the above categories, we will reduce invitations to those who are not represented in the sample. We will aim to interview carers until saturation of data is reached. We envisage this will be between 15-20 carers. Once we have achieved saturation we will cease inviting carers to take part in this component of the study. Carers will have the choice of completing this interview on the same day or another day if they are feeling tired.

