7 DATA ANALYSIS

7.1 Statistical Analysis

The statistical analysis will be overseen by the project statistician ([name]). Multivariable regression analysis will be used to enable us to explore the impact of a range of modifiable factors reflecting preparation for end of life on the MMCGI-SF, our main outcome. This type of analysis also allows us to control for potential confounding variables. The analysis will use the MMCGI-SF as the dependent variable with five predictor variables: knowledge of how dementia progresses; knowledge of the person with dementia's end of life preferences; having a lasting Power of Attorney or other formal advance directive in place; satisfaction with communication with healthcare providers; and satisfaction with support for health from your social network (detailed in Section 4.1).

The latter two items are extracted from the Health Literacy Questionnaire [28]. Health literacy is likely to be related to deprivation, which we will measure using the Townsend Deprivation Index. We will first examine whether there is collinearity between the health literacy and deprivation variables. If they are not related we will add deprivation as a covariate. Other potential confounding variables will be included in the analysis:

- Relationship type: being a spouse/partner, a child or another relationship (categorical variable; i.e. 2 covariates)
- Gender (binary measure)
- Care home status: living at home or in a care home (binary measure)
- Religiosity (continuous measure)

In total there are 10 potential covariates to be included in the model. A sample of 15 participants per covariate is preferable while ten may be sufficient.[34]. We will aim to recruit 150 participants for an adequately powered analysis.

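### Does the lack of MMCGI-SF subscale models undermine the ranking of social support among the five preparation factors?

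*Combined protocol and SAP*

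**What the plan says.** Section 4.1 chooses the MMCGI-SF to measure severity of grief before death, adds "This scale contains three subscales: heartfelt sadness and longing, worry and felt isolation, and personal sacrifice burden", and gives a cutoff for the whole scale only (70 of 90). One of the five factors is "Higher satisfaction with support for health from social network", measured by the Social Support subscale of the Health Literacy Questionnaire (HLQ).

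Section 7.1 calls the MMCGI-SF the main outcome and states: "The analysis will use the MMCGI-SF as the dependent variable with five predictor variables". It does not use the words total score, but a single dependent variable and a whole-scale cutoff imply one.

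The hypothesis in section 3.1 is that "modifiable factors indicating preparation for end of life are associated with lower grief before the death in carers of people with dementia". The relevant secondary objective in section 3.2 is "To identify which modifiable factors reflecting preparation for end of life are most strongly related to grief before the death". Section 2 says that knowing which factors are tied most tightly to "grief before the death will inform the development of a resource for carers".

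The one reference to exploratory work in section 4.1 reads "A number of other measures have been included for other exploratory analysis and to control for possible confounders". It introduces the list that follows (deprivation, anxiety and depression, closeness, coping, religiosity, experience of the study) and does not refer to the grief subscales.

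**The concern.** A predictor about support from the social network is set against an outcome that contains a subscale on isolation. If the two share content, support could outrank the other four factors because of one third of the instrument. A whole-scale coefficient does not reveal this, since it adds up the subscale coefficients. The ranking is a stated objective and feeds the design of a carer resource, so a first place for support might be read as a link with grief in general when it is mainly a link with feeling isolated. The data for subscale models will be collected anyway, which makes their absence look like an oversight.

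**Working it through.** **1. The plan's own figure.** Section 7.1 counts 5 factors + 2 (relationship type) + 1 (gender) + 1 (care home) + 1 (religiosity) = 10 covariates. At 15 participants each, 15 × 10 = 150, as stated. A subscale model would carry the same covariates, so this rule neither rules such models out nor calls for them. The question is whether the aims need them.

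**2. Aims against model.**

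| Item | Concerns | Addressed by the whole-scale model? |
|---|---|---|
| Hypothesis (3.1) | grief before the death | yes |
| Ranking objective (3.2) | grief before the death | yes |
| Main outcome (7.1) | MMCGI-SF | yes |

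No objective asks which component of grief a factor relates to.

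**3. Would an extra support-isolation correlation make the ranking wrong?** All inputs here are assumed, because the documents give no correlations. Mid setting: three equally weighted standardised subscales with intercorrelation 0.5; each factor correlates −0.20 with each subscale; factors intercorrelate 0.2; other covariates are independent of the factors; ranking is by standardised coefficient (section 7.1 names no metric).

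- SD of the total: √(3 + 6 × 0.5) = √6 = 2.449.
- Correlation of each factor with the total, no excess: 3 × (−0.20) / 2.449 = −0.245.
- With equal factor intercorrelation ρ, coefficient j is [r_j − ρ Σr / (1 + 4ρ)] / (1 − ρ). Two coefficients therefore differ by the difference in r divided by 1 − ρ.
- No excess: all five equal −0.245 / 1.8 = −0.136.
- Excess 0.1: support's r is −0.7 / 2.449 = −0.286. The coefficients are −0.181 for support and −0.130 for the others, a gap of (0.1 / 2.449) / 0.8 = 0.051.
- Excess 0.2: support's r is −0.8 / 2.449 = −0.327. The coefficients are −0.227 and −0.125, a gap of (0.2 / 2.449) / 0.8 = 0.102.

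These are population values and need only the correlations, not normal data. In both excess settings support really is the factor most strongly related to the total.

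Simulation at n = 150 used 6,000 samples in each of 27 settings, with five factors and six other covariates including deprivation (150 − 11 − 1 = 138 residual df). The ranges are over the settings.

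| Excess | Support ranks first, mid setting | Range |
|---|---|---|
| 0 | 19% | 19% to 21% |
| 0.1 | 36% | 33% to 42% |
| 0.2 | 57% | 50% to 65% |

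The first row is close to the one in five expected when five factors are equal. The other rows show a truly strongest factor being identified more often, which is not bias.

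**4. What the whole-scale model leaves open.** A broad association of −0.2 SD on each subscale gives a slope of 3 × (−0.2) = −0.6 on the sum. One of −0.6 SD on isolation and 0 elsewhere also gives −0.6. The model cannot tell these apart, but both are the same strength of relation to grief as a whole, which is what section 3.2 asks about.

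**5. The premise of overlap.** It rests on names, since item wording is not in the documents. Even the names match loosely: the factor is satisfaction with support for health, from a questionnaire that section 4.1 describes as neutral and about communicating with healthcare professionals, while the subscale joins worry to isolation. By the same reasoning, knowledge of dementia progression could be paired with worry.

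**The case for a change.** The strongest reply is that a broad link with grief and a link with isolation alone are different messages for a carer resource, and that the planned coefficient cannot separate them at any sample size. If the overlap were only shared wording, support's lead on the measured total would overstate its relation to grief as a construct. Pre-specified subscale models would cost no extra data and would be more credible than ones chosen after the ranking is seen.

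The algebraic part of this stands, and the whole-scale coefficient should not be read as saying where in grief an association sits. The rest does not make the omission a fault:

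- The question of location is not among the objectives. Nothing in the documents shows what would change in the resource if the answer were one subscale. The interviews in section 4.2 also inform the choice of supports: "It will also examine what supports they have found helpful".
- Shared wording is conjecture here, and subscale models could not separate it from a real link.
- The natural supplement compares support's coefficient for isolation with the mean of its coefficients for the other two subscales. Under the assumptions above, its 95% interval has a half-width of about 0.15 SD (0.13 to 0.19). Power is 29% (23% to 45%) for an excess of 0.1 and 84% (72% to 97%) for 0.2. An interval that includes zero would be inconclusive, so this comparison would not by itself establish a broad association. The subscale models would add 3 × 5 = 15 coefficients to report.
- The limit is in the plan and not in the data. Subscale scores can be formed from the collected MMCGI-SF and reported as exploratory.

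**Conclusion.** The concern does not hold. No subscale model is planned, but none is needed for the hypothesis, the ranking objective or the main outcome as stated. Where support has an excess correlation with isolation of 0.1 or 0.2, its true standardised coefficient on the total is larger by about 0.05 or 0.10 in size, so its higher rank is correct for the question the plan asks. Those figures rest on assumed correlations, equal subscale weights and ranking by standardised coefficient. The simulated percentages also treat every factor as normal, although the directive factor is binary and end-of-life wishes rest on two questions. The conclusion that the plan answers its own questions rests on sections 3.1, 3.2 and 7.1 and not on those figures. What remains is a preference for one more exploratory analysis.

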4.2 Qualitative semi-structured interviews (n=20)

A sub-sample of the 150 carers will be invited to participate in an additional set of semi-structured open-ended questions to enable more in-depth exploration of some of the secondary objectives as outlined in section 3.2 above. The interview will explore the dynamic and changing nature of grief over time, how carers identify with the concept of grief and whether they consider they are going through a grief experience. It will also examine what supports they have found helpful and what they perceive to be unmet information and support needs and possibly programs/resources that might address these needs. The interview guide (Appendix 3) provides a list of questions that will be used as a guide for a fluid conversation that will pick up on areas considered relevant by the participant. Qualitative interviews will be audio-recorded with permission from the participant on an encrypted digital recorder and then transcribed verbatim by the research team.

Participants will be purposively selected to provide a mix of responses representing male and female participants, adult child and spouse participants, different ethnicity as well as carers of people at

different severity of dementia. Participants who agree to participate in the quantitative interviews will also be asked to participate in the qualitative interview after completing the quantitative interview. If the sample is not representing a mix of carers based on the above categories, we will reduce invitations to those who are not represented in the sample. We will aim to interview carers until saturation of data is reached. We envisage this will be between 15-20 carers. Once we have achieved saturation we will cease inviting carers to take part in this component of the study. Carers will have the choice of completing this interview on the same day or another day if they are feeling tired.

5 ELIGIBILITY CRITERIA

5.1 Inclusion Criteria

Carers of people with dementia providing practical, social, emotional or supervisory support to a friend or family member. This will include carers of people with dementia living at home or in a care home. Carers will be 18 years of age or over and living in England. The person they care for will have received a formal diagnosis of any dementia related disease.

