5.2 Exclusion Criteria

Carers who are not able to communicate in English or who do not have capacity to provide informed written consent.

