6.1.3 Non-NHS services

Other non-NHS services including care homes, Admiral nursing services that are not attached to NHS services and branches of the Alzheimer's Society will also be invited to assist with recruitment. Recruitment through these services will be undertaken using the same approach as that used with NHS services. In addition, researchers may attend carer education/support groups to discuss the study and identify any interested carers or may promote the study via their newsletters.

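### More than one carer of the same person with dementia can enrol, and the planned regression makes no provision for correlation between co-carers (minor; probably small effect)

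*Combined protocol and SAP*

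**What the plan says.** Section 5.1 admits "Carers of people with dementia providing practical, social, emotional or supervisory support to a friend or family member". It adds: "This will include carers of people with dementia living at home or in a care home". It does not ask for a main or primary carer. Section 5.2 excludes only "Carers who are not able to communicate in English or who do not have capacity to provide informed written consent". Neither section mentions a second carer of someone already represented in the study.

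Recruitment uses several parallel routes: a self-registration website (Section 6.1.1), mailings and flyers through NHS services (6.1.2), and care homes, charity branches and newsletters (6.1.3). Section 6.1.3 also says that "researchers may attend carer education/support groups to discuss the study and identify any interested carers".

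The third of the five hypothesis predictors in Section 4.1 is whether a Power of Attorney or other directive exists, coded as "binary variable; any form of directive in place/not in place". Care home status is one of the confounders in Section 7.1.

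On analysis, Section 7.1 says: "Multivariable regression analysis will be used to enable us to explore the impact of a range of modifiable factors". The sample size comes from a participants-per-covariate rule: "In total there are 10 potential covariates to be included in the model", and "We will aim to recruit 150 participants for an adequately powered analysis". Clustering, robust standard errors and random effects are not mentioned. Section 10 gives each participant a research number and stores the data without name, address or date of birth. No code linking carers of the same person is described.

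**The concern.** A spouse and a child, or two siblings, caring for the same person can each meet the criteria and each reach the study by a different route. Directive status and care home status are facts about the person with dementia, so co-carers would normally have the same values. Their grief may also be alike, since they are responding to the same illness and the same losses.

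For a predictor that is shared in this way, two co-carers carry less information than two unrelated carers. A regression that ignores this reports too narrow an interval for that predictor. At stake is the calibration of the interval and test for predictor 3, which is part of the primary hypothesis, and of the coefficient for care home status. The interval around the prevalence of high grief (Section 3.2) would be affected in the same way. The point estimates are not the issue.

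**Working it through.** **The plan's own figure.** Section 7.1 prefers 15 participants per covariate and counts 10 covariates: five predictors, two terms for relationship type, and one each for gender, care home status and religiosity. 15 x 10 = 150, which reproduces the target. The rule counts each carer as one full unit. The documents give no effect size, standard deviation, power or significance level, so there is no power calculation to rework.

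**Inputs.** n = 150 is from Section 7.1. The following are assumptions, because the documents give no figures:
- f, the share of participants who belong to a co-carer pair: 10% to 20% as a moderate range, 5% and 40% as outer cases
- rho, the correlation of residual grief within a pair: 0.4, with 0.2 to 0.6 as the range
- a two-sided nominal 5% test

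**Predictor shared within pairs.** An unpaired carer contributes variance in proportion to 1 and a paired carer in proportion to 1 + rho. The inflation is therefore

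deff = (1 - f) + f(1 + rho) = 1 + f x rho

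The standard error is understated by 1 - 1/sqrt(deff), and the actual error rate is 2 x (1 - Phi(1.96/sqrt(deff))).

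| f | rho | deff | SE understated | Actual error of 5% test | Effective n = 150/deff |
|---|---|---|---|---|---|
| 5% | 0.2 | 1.01 | 0.5% | 5.1% | 148.5 |
| 10% | 0.4 | 1.04 | 1.9% | 5.5% | 144 |
| 20% | 0.4 | 1.08 | 3.8% | 5.9% | 139 |
| 20% | 0.6 | 1.12 | 5.5% | 6.4% | 134 |
| 40% | 0.6 | 1.24 | 10.2% | 7.8% | 121 |

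A 20% share is 30 carers in 15 pairs; a 40% share is 60 carers in 30 pairs. If co-carers report directive status differently, the predictor is not fully shared and the inflation is smaller.

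**Covariate that always differs within a pair.** For a balanced binary covariate the sign reverses: deff = 1 - f x rho. At f = 20% and rho = 0.4 this is 0.92, and the nominal 5% test runs at about 4.1%. The ordinary standard error is then too large.

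**Simulation check.** Ordinary least squares was simulated with n = 150, 10 covariates, rho = 0.4 and 6,000 replicates per setting.

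| f | Shared in pair | Opposite in pair | Unrelated in pair |
|---|---|---|---|
| 0 | 0.050 | 0.048 | 0.049 |
| 10% | 0.057 | 0.046 | 0.052 |
| 20% | 0.058 | 0.041 | 0.047 |
| 50% | 0.067 | 0.026 | 0.046 |

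The simulation standard error near 0.05 is sqrt(0.05 x 0.95/6000) = 0.003. The directions agree with the formulas. At 50% the simulated rate for a shared predictor (0.067) is a little below the formula's 0.074. A covariate unrelated within pairs stays close to 0.05.

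**The case against.** The strongest reply is that the effect may be negligible. Nothing in the documents suggests that many co-carers will enrol, and at a 5% share with correlation 0.2 the error rate is 5.1%. That stands, and it is why the point is minor.

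Three stronger readings are tempting and are not supported:

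- **That standard errors would be too small throughout.** This needs co-carers to enrol, positive residual correlation, and a predictor shared within pairs. Of the five hypothesis predictors, only the directive variable describes the person with dementia. Dementia knowledge, knowledge of wishes and the two health literacy measures belong to the carer and can differ. For relationship type, a spouse-and-child pair pushes the error the other way.
- **That the clustering could never be found.** The team telephones participants two days after the interview (Section 12.1), seeks consent for contact over the next two years (6.2) and sends a lay summary (19). Two researchers conduct the interviews (15). Dementia severity, diagnosis type, time since diagnosis and postcode are collected (4.1), and the CRF in Appendix 1 was not available for this review. Some pairs may well be recognised. What stands is that no linking code is described, so reliable linkage is not planned.
- **That a family counted twice distorts prevalence.** The objective in Section 3.2 concerns carers, so two carers rightly count as two. Only the width of the interval is affected.

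It can also be said that Section 7.1 does not rule out cluster-robust errors and that a statistician oversees the analysis. That is true, but such errors need a linking variable, and the plan provides none.

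**Conclusion.** The point holds as a minor one. The plan lets co-carers enter, does not describe how they would be linked, and does not say how the regression would handle them. If they enrol with positively correlated residual grief, inference could be anti-conservative for directive status and care home status, and conservative for covariates that differ within a pair.

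Under the moderate assumptions (10% to 20% of participants in pairs, correlation 0.4) the standard error of a shared predictor is 2% to 4% too small, and a 5% test runs at 5.5% to 5.9%. Reaching about 7.8% takes a 40% share and a correlation of 0.6, which nothing in the documents supports. The true share and correlation are unknown, so the actual effect could be nil. The case for acting is that the remedy costs almost nothing and the link is most reliably recorded at enrolment.

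**What to change.** - **Section 6.2:** at the telephone screen, ask whether another carer of the same person with dementia has taken part or plans to.
- **CRF:** give such carers a shared family code. An arbitrary number is enough and is compatible with the de-identified storage in Section 10.
- **Section 7.1:** use cluster-robust standard errors by that code for the regression and for the interval around the prevalence of high grief. Add a sensitivity analysis with one carer per person with dementia, and report the number of linked carers. With 15 pairs there would still be 150 - 15 = 135 clusters.

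The cost is one screening question, one CRF field and a little more analysis; no carer is turned away. Limiting Section 5.1 to one carer per person with dementia is an acceptable alternative and keeps the analysis simpler, but it would turn away some eligible carers.
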